2.1.2 Reporting Conventions

The formats for the tables, listings, and figures described in this SAP will be provided in a companion document. Changes to the formats of these reports that are decided after the finalization of the SAP will not require an amendment. In addition, any additional supportive or exploratory analyses requested after SAP approval will not require amendment of the SAP. These additional analyses will be described in the CSR.

Study data from the eCRFs as well as derived variables will be provided in subject data listings. An indication of specific listings for each data type will not be indicated in the text of subsequent SAP sections. Data listings supplied as part of the CSR will be sorted by study site number concatenated with subject number, treatment group, assessment dates, and/or time point.

The following conventions will be applied to all data presentations and analyses:

- Confidence intervals (CIs) will be two-tailed and constructed at a confidence level of 95%. Statistical tests will be performed at a significance level of 5%, and p-values will be two-sided, unless otherwise specified.
- Quantitative variables will generally be summarized by the number of subjects, mean, standard deviation, median, minimum, and maximum. Unless otherwise specified, the minimum and maximum values will be displayed to the same number of decimal places as the raw data, the mean and median will be presented to one extra decimal place compared to the raw data, and the standard deviation will be displayed to two extra decimal places compared to the raw data.
- Categorical variables will be summarized by the number and percentage of subjects (and number of events where appropriate) within each category. Unless otherwise specified, the percentage will be presented in parentheses to one decimal place. Frequency and percentage values of 0 will be presented as '0' rather than '0 (0)'.
- All summary tables will include the analysis population sample size (i.e., number of subjects) in each treatment group.
- Date variables will be formatted as DDMMYYYY for presentation.

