2.4.3 Primary Effectiveness Analysis

Responder rate based on the GJS, as assessed live by the Blinded Evaluator at 3 months after baseline, will be the primary effectiveness endpoint. A responder will be defined as a subject with at least 1 grade improvement from baseline on both sides of the face concurrently.

The null hypothesis will be that there is no relationship between responder rate and treatment group (i.e., the responder rate is the same in treated and untreated subjects). The alternative hypothesis will be that there is a relationship between responder rate and treatment group (i.e., the responder rate is different in treated subjects compared to untreated subjects).

[figure not shown]
The estimates of the responder rate in each treatment group will be presented as well as the difference in responder rates. Corresponding confidence intervals for responder rates (via Clopper-Pearson) and the difference in responder rates (via normal approximation) along with the p-value (via Fisher's exact test) for the difference will also be presented.

First, the Breslow-Day test for homogeneity of odds ratios will be used to assess consistency of GJS odds ratios across all injection tool strata (the needle-treated group, the cannula-treated group,

[figure not shown]

and the combination group). A significance level of 0.05 will be used to determine if the responder rates are non-homogenous. If the Breslow-Day p-value is less than or equal to 0.05, the primary analysis will be stratified (i.e., conducted separately) for the needle-treated group, the cannula-treated group, and the combination group, using a significance level of 1.7% to account for multiplicity. If the Breslow-Day p-value is greater than 0.05, the analysis will be carried out on pooled groups, using a significance level of 5%. Regardless of whether the primary analysis will be based on pooled injection tool groups, or done separately, the no treatment control group subjects will be pooled across all study sites. In either case, the primary analysis will be repeated in each injection tool stratum as part of the pre-planned subgroup analyses (see SAP Section 2.4.5).

In order to assess the poolability of study sites, a Breslow-Day test for homogeneity of odds ratios across sites will be performed. Regardless of results, the primary analysis will be repeated for each study site as part of the pre-planned subgroup analyses (see SAP Section 2.4.5).

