2.7.4 Calculations

A two-sided test at the 5% significance level will have more than 99% power to demonstrate a difference between a responder rate of 70% in the GP0109 group and a responder rate of 32% in the no treatment control group when the sample sizes are 150 and 50, respectively.

Performing the same test, but in needle, cannula, and combination subjects separately (at the 1.7% level of significance for each test to account for multiplicity), the power will be approximately 90% (assuming the same responder rate of 70% in all GP0109 groups (needle, cannula, and combination). All no treatment control group subjects will be included in each of the by strata tests.

Accounting for approximately 10% dropouts at 3 months after baseline, approximately 224 subjects need to be randomized in a 3:1 ratio (GP0109 to no treatment control group).

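### In the separate-tool branch, Holm's step-down test would hold the same 5% family error as the fixed 1.7% per tool and give a weaker tool a better chance: a cheap improvement, not an error

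*SAP*

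**What the plan says.** SAP 2.4.3 chooses the form of the primary analysis with a Breslow-Day test across the three injection tools. "If the Breslow-Day p-value is less than or equal to 0.05, the primary analysis will be stratified", meaning one comparison per tool, "using a significance level of 1.7% to account for multiplicity". Otherwise all treated subjects are pooled and tested at 5%. In both branches the untreated controls are pooled, so the three tool tests share one control group. Protocol 10.4.1 and the protocol synopsis give the same rule.

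SAP 2.7.4 repeats it for the power statement, "at the 1.7% level of significance for each test to account for multiplicity", and quotes about 90% power per tool, "assuming the same responder rate of 70% in all GP0109 groups". SAP 2.1.2 adds that "p-values will be two-sided, unless otherwise specified".

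The readable text describes no ordering of the three tests and no passing on of unused significance level. Neither document says whether success in this branch needs one, some or all tools, and neither gives a planning rate for a tool that does less well.

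**The concern.** A fixed threshold for each of three tests ignores what the other two show. Once two tools have been declared effective, only one hypothesis remains open, and the family error of 5% no longer requires that last test to be held to 1.7%.

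Holm's procedure uses this. The smallest p-value is tested at 5%/3, the next at 5%/2 and the largest at 5%, stopping at the first failure. It controls the family error under any dependence, including the dependence created by the shared controls.

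The branch opens only when the tools appear to differ. A common picture there is two clear successes and one weaker tool, which is where the fixed threshold costs most. What is at stake is the formal result for that weaker tool: with p = 0.03 after two successes, it fails under the plan and passes under a rule with the same 5% guarantee.

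**Working it through.** **Inputs from the documents.** Separate-tool level 1.7%, branch trigger 0.05, Fisher's exact test (SAP 2.4.3), two-sided (SAP 2.1.2). Rates of 70% and 32%, with 150 treated and 50 controls evaluable, so 50 per tool against all 50 controls (SAP 2.7.4). About 56 randomized per tool and 56 to control (SAP 2.7.1).

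**Assumptions not in the documents.** The weakest tool's rate (55%, varied below), rates of 70% or 80% in the other two, and controls split almost equally over the tools for the Breslow-Day test (19/19/18).

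**1. The plan's own figure.** Power = sum over a and c of Bin(a; 50, 0.70) x Bin(c; 50, 0.32), taken where the Fisher p-value is at most 0.017. Result: 91.8%, against the stated figure of about 90%. The pooled test, 150 vs 50 at 5%, gives 99.7%, against more than 99%. Both reproduce.

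**2. Thresholds.** Plan: 3 x 1.7% = 5.1%. Holm: 5%/3 = 1.67%, 5%/2 = 2.5%, then 5%. Holm's slightly lower first step costs almost nothing: power of a single test at 1.67% is still 91.8% with 50 per group.

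**3. Gain if the tool tests were run in every trial** (50 per group, other two tools 70%, control 32%, exact calculation):

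| Weakest tool | Fixed 1.7% | Holm | Gain (points) |
|---|---|---|---|
| 70% | 91.8% | 94.7% | 2.9 |
| 65% | 80.3% | 87.2% | 7.0 |
| 60% | 62.6% | 74.5% | 11.9 |
| 55% | 42.1% | 56.9% | 14.8 |
| 50% | 23.7% | 37.4% | 13.7 |
| 40% | 3.9% | 9.1% | 5.1 |

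Gains are taken before rounding. The gain peaks at 14.9 points near 53-54%. With the other two tools at 85% and the weakest at 55%, it is 16.4.

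**4. Gain under the plan's actual rule.** The tool tests are primary only when the Breslow-Day p-value is 0.05 or less. Simulation with 56 per tool and 56 shared controls (400,000 trials per row):

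| Tool rates vs 32% | Branch opens | Weakest tool in branch, fixed 1.7% | Same, Holm | Gain in branch (points) | Gain over all trials (points) |
|---|---|---|---|---|---|
| 70/70/70 | 5.2% | 91.9% | 95.5% | 3.6 | 0.052 x 3.6 = 0.2 |
| 70/70/55 | 12.8% | 29.9% | 45.2% | 15.3 | 0.128 x 15.3 = 2.0 |
| 80/80/55 | 31.6% | 32.7% | 48.9% | 16.2 | 0.316 x 16.2 = 5.1 |

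Repeat runs agree to within about a point (45% to 46% for the Holm figure in the second row). In the third row both stronger tools have already passed 1.7% in 99.6% of branch trials. With 50 per group, the branch figures for the second and third rows are 26.8% to 40.8% and 28.9% to 44.8%. If 10% missing is scored as non-response (72/72/49.5 vs 28.8), the branch figure moves from 23.5% to 39.0%.

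**5. Error.** Tools at 80/80/32 vs 32% (third tool ineffective), 56 per group, tests run in every trial: the chance of a false claim for the third tool is about 1% under the fixed rule and 3.2% under Holm. With no tool effective, the family error is below 3% under both rules.

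**The case against.** The strongest reply is that nothing here is broken. A fixed 1.7% is a pre-specified, conventional rule, the sample size was justified with it, and the stated power reproduces. That stands: this is a question of efficiency. The sum of 5.1% is rounding, and because Fisher's test is conservative the simulated family error stays well below 5%.

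The size is also conditional, which stands too. A reader might infer that the weakest tool simply loses about 15 points of power. The documents do not support that. Their only planning rate is 70% in every tool, where the gain is about 3 points. Fifteen is close to the maximum and needs a true rate near 55%. Most trials would never run these tests as the primary analysis.

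A reader might also infer that use of a tool that misses 1.7% would go unsupported. The indication is not specific to a tool, no such consequence is stated, and SAP 2.4.3 and 2.4.5 report the per-tool comparisons whichever branch is taken.

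Finally, Holm makes a claim for an ineffective third tool about three times as likely (about 1% to 3.2%). A sponsor could reasonably prefer the stricter evidence, although 3.2% is still within the 5% guarantee. Holm also does not correct for selection by the Breslow-Day test: given entry to the branch with no effective tool, the family error is about 5.7% under either rule (50 per group).

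**Conclusion.** The point holds as a cheap improvement to a valid rule. Holm's test gives the same 5% family guarantee, keeps essentially every rejection the fixed 1.7% would make, and adds others. Inside the branch, with a weakest tool near 55% against 32% in controls, the gain is about 15 to 16 points. At the planned equal rates it is about 3. Over all trials it runs from about 0.2 to 5 points in the scenarios examined. The rate for the weakest tool is an assumption throughout. The documents do not support calling the plan's error control defective, or attaching a consequence for use or labelling to a tool that misses 1.7%.

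**What to change.** In SAP 2.4.3, Protocol 10.4.1 and the synopsis, replace the fixed 1.7% with Holm's procedure: order the three tool p-values, test them at 1.67%, 2.5% and 5%, and stop at the first that is not significant. State that each tool is its own claim, which also settles what counts as success in this branch.

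Keep the power of roughly 90% per tool in SAP 2.7.4, Protocol 10.11.4 and the synopsis, and say that it is the conservative first-step figure.

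The cost is a short edit in each place and no new subjects or data. It should be made before results are known. SAP 2.1 provides for amendment before database lock, and the protocol change follows Protocol 12.3, with ethics and regulatory review where applicable. Two downsides should be accepted openly: Holm has no simple matching simultaneous intervals, so the per-tool intervals are reported apart from the decision, and the chance of a false claim for an ineffective third tool rises as shown above.

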4.4 Randomization and blinding

4.4.1 Randomization

Approximately 224 subjects will be randomized in a 3:1 ratio to treatment with GP0109 or no treatment. Before starting the study, a computer-generated randomization list will be prepared under the supervision of a designated statistician from the Sponsor. The randomization list will be stratified by injection tool (needle, cannula, and combination) and FST group (I-III, IV, and V-VI). The FST I-III group will be further stratified by study site. Randomization numbers will be allocated in ascending sequential order to each subject. Randomization will be performed using an Interactive Response System by assigning each subject to GP0109 or no treatment according to the randomization list.

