10.4 Effectiveness analysis

10.4.1 Primary effectiveness analysis

Responder rate based on the GJS, as assessed live by the Blinded Evaluator at Month 3 after baseline, will be the primary effectiveness endpoint. A responder will be defined as a subject with at least 1 grade improvement from baseline on both sides of the face concurrently.

The null hypothesis will be that there is no relationship between responder rate and treatment group (i.e. the responder rate is the same in treated and untreated subjects). The alternative hypothesis will be that there is a relationship between responder rate and treatment group (i.e. the responder rate is different in treated subjects compared to untreated subjects).

The estimates of the responder rate in each treatment group will be presented as well as the difference in responder rates. Corresponding confidence intervals for responder rates and the difference in responder rates along with the p-value for the difference will also be presented.

First, the Breslow-Day test for homogeneity of odds ratios will be used to assess consistency of GJS odds ratios across all strata (the needle-treated group, the cannula-treated group, and the combination group). A significance level of 0.05 will be used to determine if the responder rates are non-homogenous. If the Breslow-Day p-value is less than or equal to 0.05, the primary analysis will be stratified (i.e. conducted separately) for the needle treated group, the cannula-treated group, and the combination group, using a significance level of 1.7% to account for multiplicity. If the Breslow-Day p-value is greater than 0.05, the analysis will be carried out on

GALDERMA <small>EST. 1987</small>	Title CTN 43BBJ1911 US Jawline, Clinical Investigation Plan
---	--

pooled groups, using a significance level of 5%. Regardless of whether the primary analysis will be based on pooled injection tool groups, or done separately, the no treatment control subjects will be pooled across all study sites. Fisher’s exact test will be used to compare the responder rates between the treated and untreated subjects at Month 3.

In order to assess the poolability of study sites, a Breslow-Day test for homogeneity of odds ratios across sites will be performed. If the p-value of the sites test is <0.05, then subgroup analysis by study sites will be done.

CCI

CCI

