1.1.2 Number of Subjects and Randomization

Approximately 224 subjects will be randomized (3:1) to either a GP0109 treatment group or to a no treatment control group. At least 45 subjects will be Fitzpatrick skin type (FST) IV through VI. This includes at least 23 subjects with FST V-VI, where at least 12 subjects will be FST V and at least 11 subjects will be FST VI.

Approximately 15 sites are planned for the study, with approximately 5 sites using needle for injection, approximately 5 using cannula for injection, and approximately 5 with a combination of needle and cannula for injection. The aim is to achieve an even distribution of subjects between the assigned sites.

In the GP0109 treatment group, approximately 56 subjects will receive injection with needle, 56 with cannula, and 56 with both needle and cannula combined. Approximately 56 subjects will be randomized to a no treatment control group at baseline.

Details of the enrollment to be conducted in two stages follow:

- Stage 1: will include the first approximately 50 eligible subjects randomized. At least 10 of these subjects will be FST IV-VI, where at least 3 subjects will be FST V and at least 2 subjects will be FST VI. The aim is to achieve an even distribution of subjects to a minimum 1 site using needle for injection, 1 site with cannula for injection, and 1 site with combination of needle and cannula for injection.
- Stage 2: will include approximately 174 eligible subjects.

The subject randomization list for each stage will be stratified by injection tool (needle, cannula, and combination) and FST group (FST I-III, FST IV, and FST V-VI). The FST I-III group only will be further stratified by study site. Study sites are assigned in advance to 1 of the 3 injection tool categories.

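### Free improvement: randomization is stratified by injection tool and FST group, but the pooled primary test and interval are unstratified, which costs a little calibration and precision

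*SAP*

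**What the plan says.** **Design.** SAP 1.1.2: "The subject randomization list for each stage will be stratified by injection tool (needle, cannula, and combination) and FST group". Protocol 4.4.1 gives the FST levels: "The randomization list will be stratified by injection tool (needle, cannula, and combination) and FST group (I-III, IV, and V-VI"). Both documents add site as a stratum within FST I-III only. Each site uses one injection tool, so the tool strata are also separate sets of sites.

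**Analysis.** SAP 2.4.3 and Protocol 10.4.1 first run a Breslow-Day test across the three tools.

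- p above 0.05: "If the Breslow-Day p-value is greater than 0.05, the analysis will be carried out on pooled groups, using a significance level of 5" percent.
- p of 0.05 or less: "If the Breslow-Day p-value is less than or equal to 0.05, the primary analysis will be stratified (i.e., conducted separately") by tool, "using a significance level of 1.7% to account for multiplicity".

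In this plan, stratified means three separate tests. It does not mean one test that combines evidence across strata. In both branches controls are pooled over all sites, and hence over all tools. The protocol's Fisher's exact "test will be used to compare the responder rates between the treated and untreated subjects at Month 3". SAP 2.4.3 adds a normal-approximation interval for the difference. SAP 2.1.2 states that "p-values will be two-sided, unless otherwise specified".

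FST does not appear in either branch; it returns only as a two-level subgroup factor in SAP 2.4.5. Site is used for a homogeneity test and subgroup tables.

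**The concern.** When randomization is balanced within strata that predict response, an unstratified comparison carries between-stratum variation that the design has already removed. The usual standard error is then too large, and the test rejects less often than its nominal level. A stratified test and a stratum-weighted difference use the same data and recover that precision.

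Strata could matter here. The tools are used at different sites with different raters, and the endpoint is a live rating on a scale for which SAP 2.7.2 says no earlier data exist. The stake is the calibration of the p-value, the width of the interval, and some power if the true effect is smaller than planned.

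**Working it through.** **1. The plan's own figures (SAP 2.7.4).** Power = Φ[(Δ − z·SE₀)/SE₁], with SE₀ from the pooled rate and SE₁ from the separate rates; Δ = 0.70 − 0.32 = 0.38.

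- Pooled, 150 vs 50, 5%: pooled rate (105 + 16)/200 = 0.605; SE₀ = 0.0798; SE₁ = 0.0758; Φ[(0.38 − 1.960 × 0.0798)/0.0758] = 99.8% (exact Fisher 99.7%). The plan says more than 99%.
- By tool, 50 vs 50, 1.7%: pooled rate 0.51; SE₀ = 0.1000; SE₁ = 0.0925; Φ[(0.38 − 2.387 × 0.1000)/0.0925] = 93.7% (exact Fisher 91.8%). The plan says about 90%.
- N: 200/0.9 = 222.2, so 223. The plan says about 224.

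All three reproduce.

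**2. Type I error with no strata effect.** Exact enumeration of the two-sided Fisher test at 168 vs 56 and a common 32% rate gives 4.2% (3.9-4.5% for rates from 10% to 60%). The pooled chi-square test gives 4.9%. This shortfall is due to discreteness alone.

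**3. Type I error with strata effects.** Simulation: 200,000 trials per row, nine tool × FST cells, 3:1 in each, 48 of 224 subjects in FST IV-VI. The documents give no rates by stratum, so every rate below is an assumption. With T treated, C controls, n = T + C, x treated responders and m responders in a cell, CMH = [Σ(x − Tm/n)]² / Σ[TCm(n − m)/(n²(n − 1))].

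| Null rates (assumed) | Pooled Fisher | Pooled chi-square | CMH | Whole two-branch rule |
|---|---|---|---|---|
| 32% throughout | 4.2% | 4.9% | 4.9% | 4.3% |
| Tool 27/32/37% | 4.2% | 4.9% | 5.0% | 4.6% |
| Tool 22/32/42% | 3.9% | 4.6% | 5.0% | 5.1% |
| FST 27% vs 52% | 3.7% | 4.4% | 5.0% | 3.8% |
| Tool 12/32/52% | 3.0% | 3.6% | 4.9% | 6.9% |
| Large tool and FST effects | 2.5% | 3.0% | 5.0% | 5.3% |

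At tool rates 15/32/50% (168 vs 57) pooled Fisher rejects 3.2%. The mean unstratified standard error there is 0.0712 against a true 0.0683, a ratio of 1.042.

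**4. Interval.** Under the null the pooled interval covers 94.5-95.0% with no to moderate strata effects and 95.9-96.5% with large ones. The Mantel-Haenszel interval covers about 94.4% throughout. Mean widths, pooled vs stratified: 0.280 vs 0.280 with no effect, 0.280 vs 0.275 at 22/32/42%, 0.280 vs 0.262 at 12/32/52%.

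**5. Power.** At a common odds ratio matching 70% vs 32%, power is 98.9-99.9% for pooled Fisher and 99.6-99.9% for CMH. At an odds ratio of 2.5 CMH gains 0.6 points with strata alike, 1.8 at 22/32/42% and 4.6 at 15/32/50%. With an FST gradient added to the last case, power went from 69.4% to 75.5% (6.1 points); treat that one as illustrative.

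**6. Why the whole rule can exceed 5%.** At 12/32/52% with no treatment effect, the pooled control rate is (12 + 32 + 52)/3 = 32%. The first tool's treated subjects respond at 12%, so the separate branch sees a 20-point difference that is purely between tools. Breslow-Day selects that branch 4.99% of the time, and at least one test then rejects 80.8% of the time: 0.0499 × 0.808 = 4.0 points. The pooled branch contributes the other 2.9 of the 6.9%.

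**7. Same-tool controls.** About 50/3 ≈ 17 controls per tool. Pooled rate (35 + 5.44)/67 = 0.604; SE₀ = 0.1373; SE₁ = 0.1304; Φ[(0.38 − 2.387 × 0.1373)/0.1304] ≈ 66%, against 93.7% by the same formula with 50 shared controls.

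**The case against.** Fisher's test is a common and safe choice, and in the pooled branch its error is conservative. The large effects need control rates near 50% for one tool. SAP 2.7.3 assumes a maximum of 32% and cites almost 30% as the most seen so far. Controls are not injected, so tool can matter for them only through site and rater differences, for which no figures are given. The stratified interval is narrower, but its coverage is slightly under nominal. All of this stands, and it is why the point is an improvement and not an error.

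A reader might infer three stronger things that the documents do not support:

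- *That ignoring the strata is why the test runs below 5%.* The rate is 4.2% with no strata effect at all, and unstratified chi-square gives 4.9%.
- *That the plan ignores its strata altogether.* Tool drives the Breslow-Day gate and the 1.7% branch, and SAP 2.4.3 repeats the primary analysis within each tool and site. Only FST, and site within FST I-III, are absent from both branches. SAP 2.4.4 is redacted and SAP 2.8 says analyses were added there, so a supportive stratified analysis cannot be ruled out. The primary method itself is fully visible.
- *That the primary procedure as a whole is conservative.* Under assumed tool differences it can exceed 5%.

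**Conclusion.** The mismatch is real and cheap to remove. In the pooled branch neither the test nor the interval uses the randomization strata. The cost is small: about 0-0.5 points of type I error beyond Fisher's own shortfall for small or moderate strata effects, and 1.2-1.7 points for large ones. The gain from stratifying is calibration, a narrower interval if strata are prognostic, and roughly 0.6-1.8 points of power (modest strata effects) or 4-6 points (large) at an odds ratio of 2.5. At the planned effect the trial's conclusion does not depend on it.

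The more consequential detail is in the separate branch. Shared controls break the within-tool randomization and can take the overall error to about 5.1-6.9% when responder rates differ by tool.

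These sizes rest on assumed rates by stratum, an assumed FST mix and homogeneous odds ratios. Site strata were not simulated.

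**What to change.** In SAP 2.4.3 and Protocol 10.4.1:

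1. In the pooled branch, make the primary test a CMH test stratified by injection tool × FST group (I-III, IV, V-VI). Report the Mantel-Haenszel risk difference, Σw·d/Σw with d the cell difference and w = TC/n, with its 95% CI. Keep unstratified Fisher as a sensitivity analysis.
2. State that site within FST I-III is left out because those cells are sparse: (224 − 45)/15 ≈ 12 subjects per site, about 3 of them controls. The smaller FST cells are sparse too (about 6 treated and 2 controls), but CMH held 4.9-5.0% with them included.
3. Say whether the Breslow-Day gate and the 1.7% branch remain. If they do, acknowledge that shared controls can raise the overall error. If same-tool controls replace them, restate the by-tool power, since about 90% would no longer apply (about 66% by the arithmetic above).

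At minimum, pre-specify the stratified analysis as a sensitivity analysis. The cost is SAP and protocol wording and one more SAS procedure statement, with no extra subjects or data. SAP 2.1 provides for amendment before database lock.
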